### 10.2.2 Criteria for evaluation

For each method ("pre-treatment" and "post-treatment"), comparisons between the treated and untreated areas will be performed to characterise the speed and extent of barrier repair.

### 10.2.3 Handling of dropouts and missing data

Only observed data will be analysed for the efficacy analysis. Subjects who withdraw from the study early will be included in the statistical analysis up to the point of when they withdraw. Since each subject acts as their own control for both the pre- and post-treatment methods, any bias that may usually be introduced by subject withdrawals should be minimal.

### 10.2.4 Interim analysis

An interim analysis is not planned for this study.

# 10.3 Statistical Methods and Analytical Plan

More details of the proposed statistical analysis will be documented in the statistical analysis plan (SAP), which will be written following finalisation of the protocol and prior to database lock and analysis.

### 10.3.1 Demographic and baseline characteristics

Continuous demographic and baseline parameters will be summarised by the number of non-missing observations, mean, standard deviation, median, minimum, and maximum. Categorical parameters will be summarised by frequencies and percentages.

# 10.3.2 Subject Disposition

Study completion status and reasons for discontinuation will be summarised by frequencies and percentages.

# 10.3.3 Efficacy

Since this an exploratory method development study, a number of different parameters are being evaluated in various ways, in order to ascertain the most sensitive measure to use in future studies.

### "Pre-Treat" Method:

Using the methodology described in Lu et al [Lu et al., 2014], utilising Fick's first law of diffusion and the fact that the thickness of the SC is approximately proportional to the cumulative SC protein removed by tape stripping, a random coefficients model will be fitted with 1/TEWL as the response variable and fixed effect model terms for cumulative protein, treatment (treated or untreated) and the protein\*treatment interaction, and random coefficients for subject\*treatment and the subject\*treatment\*protein interaction. Cumulative protein (p) will be obtained at prestripping (where p will be set to 0), and after 5, 10, 15 and 20 strips have been removed. The relative barrier quality will be determined from the slopes of the 1/TEWL vs. p relationship. The relative SC thickness will be determined from extrapolation of the linear regression lines for each treatment group to where each intercepts the x-axis (cumulative protein axis). This analysis will be performed for each visit day (day 0, 3, 5, 7, 10, 12 and 14). The day 0 analysis will give a measure of the baseline values of slope and x-axis intercept in each of the treated and untreated areas. The use of a simple linear regression model does have some drawbacks, including the overestimate of the SC thickness (or total SC protein) as 1/TEWL does not reach 0 when all the SC is removed from the skin. However, since the aim of the study is to determine the relative difference in SC thickness and barrier quality between treated and untreated skin, the simple linear model approach is sufficient (Lu et al., 2014).

From each of these random coefficients models, individual subject estimates of slope and x-intercept will be obtained. The individual subject by treatment estimates for slope and x-intercept on each post-baseline visit day (day 3, 5, 7, 10, 12 and 14) will subsequently be analysed using a repeated measures model with factors for treatment, day and treatment\*day (fixed effects) and subject (random effect), and a covariate for the corresponding baseline estimate of slope or x-intercept (obtained from the estimates at Day 0). Treatment differences will be presented at each day with 95% confidence intervals, together with p-values.

On each post baseline visit day (day 3, 5, 7, 10, 12 and 14), the change in TEWL value from prestripping to post-stripping (after 20 strips have been removed) will be calculated and compared between treated and untreated groups. A repeated measures model will be fitted with factors for treatment, day and treatment\*day (fixed effects) and subject (random effect), and a covariate for the change from pre-stripped TEWL to post-stripped TEWL assessed at the baseline visit (Day 0). The change from pre-stripped TEWL to post-stripped TEWL on Day 0 will provide a baseline measure of barrier strength of the skin when it is challenged. Treatment differences will be presented at each treatment day with 95% confidence intervals, together with p-values. A stronger barrier will result in a smaller increase in TEWL.

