# 10 Data Analysis Methods

All statistical tests will be two-sided with a significance level of 0.05 unless stated otherwise.

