# **10.1 Sample Size Determination**

This is an exploratory method development study to determine the best approach to assess barrier repair. Based on Lu et al [Lu *et al.*, 2014], in subjects with dry skin, the mean slope of 1/TEWL versus cumulative protein removed was -3.4 x 10^-5 (standard deviation (SD) approx. 1.4 x 10^-5). The mean total protein removed from SC was 3985µg (SD approx. 1150). Since the proposed study is a split-body design, the variability of the paired differences is required. It will be assumed that the correlation between the treated and untreated responses within a subject is 0.5, so that the SD of the paired differences will be the same as the SD between subjects.

Assuming that the untreated sites in the proposed study behave the same as the dry skin cohort in Lu et al [Lu *et al.*, 2014] with regards to response and variability of response, then a study with N=20 subjects will have 90% power to show a difference in slopes of 1/TEWL vs. Cumulative protein removal (treated versus untreated) of 1.1 x 10^-5, or approximately 32% of an untreated dry skin 1/TEWL vs. Cumulative protein removal slope, at the 2-sided 5% significance level.

Similarly, for the cumulative protein removed endpoint, N=20 subjects will have 90% power to show a difference (treated versus untreated) of 880 microgram (μg), or approximately 22%, at the 2-sided 5% significance level.

In summary, N=20 subjects will have 90% power to show a difference between treated and untreated groups of 32% in barrier quality (as defined by the slope) and 22% in SC thickness (as defined by the total protein intercept of the regression vs. 1/TEWL).

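### Slope and x-intercept tests treat shrunken model predictions as observed data, so their confidence intervals are too narrow by an amount set by an unstated reliability

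*Protocol*

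**What the plan says.** Protocol section 10.3.3 (Efficacy, Pre-Treat Method), repeated under Statistical Methods in the Study Synopsis, sets out two stages.

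- **Stage 1**, fitted separately for each visit day. The response is 1/TEWL. Fixed terms are cumulative protein, treatment and their interaction, so each treatment has its own mean line. Intercepts and protein slopes are random for each subject-by-treatment area. Each line rests on five readings (0, 5, 10, 15 and 20 strips).
- **Hand-off.** "From each of these random coefficients models, individual subject estimates of slope and x-intercept will be obtained".
- **Stage 2.** The post-baseline estimates "will subsequently be analysed using a repeated measures model with factors for treatment, day and" their interaction, a random subject effect and the Day 0 estimate as covariate. Treatment differences are reported by day with 95% confidence intervals and p-values.

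No weighting, shrinkage correction or carry-over of stage 1 uncertainty is stated. Section 10 adds: "All statistical tests will be two-sided with a significance level of 0.05 unless stated otherwise". Section 10.1 powers the study only for the slope and the total-protein intercept, claiming for the slope that "a study with N=20 subjects will have 90% power to show a difference in slopes" of the stated size. The opening of section 10.3.3 says the aim is to find the most sensitive measure for later studies.

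**The concern.** Individual coefficients taken from a random coefficients model are predictions, not observations. Each is pulled toward its group's mean line, and the pull grows as the line becomes noisier. Here the group is the treatment on that day. The shrinkage therefore removes spread within each treatment but does not pull the two treatment means together. A model that takes the predictions as data sees the right slope difference with too little scatter around it.

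Two things are at stake. The intervals and p-values for barrier quality and stratum corneum thickness, the two quantities used to size the study, would look more precise than the data warrant. In addition, the TEWL-change analyses in the same section (after 20 strips in the Pre-Treat method, and from the stripped value in the Post-Treat method) use raw values and carry no such gain. The comparison of measures, which is the purpose of the study, would then be uneven.

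**Working it through.** **1. The plan's own figure.** Inputs from section 10.1: N = 20 pairs; slope mean -3.4e-5, SD 1.4e-5, difference 1.1e-5; total protein mean 3985 µg, SD 1150, difference 880 µg. Because "It will be assumed that the correlation between the treated and untreated responses within a subject is 0.5", the SD of the paired differences equals the between-subject SD. Paired t-test, 19 df, two-sided 5%, critical value 2.093:

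- Slope: 1.1/1.4 = 0.786; times √20 gives noncentrality 3.51; power 91.5%.
- Total protein: 880/1150 = 0.765; times √20 gives 3.42; power 90.1%.

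The stated 90% reproduces. The issue is the later analysis, not this calculation.

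**2. What shrinkage does to the slope test.** Let b be the least-squares slope of one subject-area line, m the mean slope of its treatment on that day, and λ the reliability (true slope variance divided by true plus error variance). In balanced data, looking at the slope alone, the predicted slope is about m + λ(b − m).

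- Mean of treated minus untreated: unchanged.
- SD of the paired differences, and so the standard error: multiplied by λ.
- t-statistic: multiplied by 1/λ.
- True two-sided rate at nominal 5%: 2·P(T19 > λ × 2.093).

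| λ (assumed) | λ × 2.093 | Formula | Formula and simulations, paired per-day test |
|---|---|---|---|
| 0.99 | 2.072 | 5.2% | about 5% |
| 0.95 | 1.988 | 6.1% | about 6% |
| 0.90 | 1.884 | 7.5% | 7-8% |
| 0.80 | 1.674 | 11.0% | 11-12% |
| 0.70 | 1.465 | 15.9% | 16-18% |
| 0.60 | 1.256 | 22.4% | 22-26% |

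**3. The planned stage 2 model.** Null simulation, 500 runs per setting: 20 subjects, two areas, seven days and five readings per line, with the protocol's means, SDs and correlation of 0.5. Prediction was done per day, followed by stage 2 with treatment, day, their interaction, random subject and the Day 0 covariate. Assumptions not in the protocol: 20 strips remove 60% of the mean total protein, the quoted slope SD is free of measurement error, and the residual SD s of 1/TEWL is as listed.

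With equal steps of 0.6 × 3985/4 = 597.75 µg, the sum of squares of protein is 10 × 597.75² = 3.573e6, and λ = (1.4e-5)² / [(1.4e-5)² + s²/3.573e6]. For s = 0.01 this is 1.96e-10/(1.96e-10 + 0.28e-10) = 0.88. For scale, the mean line starts at 3.4e-5 × 3985 = 0.135, so s = 0.01 is about 7% of that value.

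| s | λ | SE ratio, predicted to least squares | Slope, predicted | Slope, least squares | x-intercept, predicted | x-intercept, least squares |
|---|---|---|---|---|---|---|
| 0.003 | 0.99 | 0.99 | 4.7% | 4.4% | 5.2% | 4.8% |
| 0.006 | 0.95 | 0.94 | 6.0% | 5.0% | 6.9% | 5.3% |
| 0.010 | 0.88 | 0.86 | 9.4% | 5.7% | 8.9% | 5.4% |
| 0.015 | 0.76 | 0.74 | 14.0% | 4.8% | 13.2% | 8.7% |
| 0.020 | 0.64 | 0.62 | 19.4% | 4.7% | 19.2% | 9.1% |

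**4. Check with a fitted REML mixed model.** With protein amounts differing between areas (400 data sets, paired test on one day), predicted slopes rejected in 13.5% and least-squares slopes in 5.5%. The ratio of their standard errors was 0.79.

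**5. The x-intercept.** The direction is the same, but it is minus the intercept divided by the slope, a heavy-tailed ratio. Unshrunken values also misbehave at low reliability (last column), so shrinkage is not the whole cause.

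**The case against.** The strongest reply is that the size is unknown. It depends on the reliability of a five-point line, which the protocol does not give. Section 8.2 averages duplicate TEWL readings and asks for one operator, both of which tend to raise it. Near 0.99 the effect is negligible. This stands, so the result has to be shown as a range that includes the harmless end.

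Second, the study is exploratory method development, with no confirmatory claim about the product. This also stands and lowers the priority. It does not remove the point, because choosing between measures is what the results are for.

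Third, the text does not name the estimator, and section 10.3 defers detail to an analysis plan that is not shown. This stands only as a caveat. The protocol fixes both models and says the individual values come from the first, and predicted coefficients are the natural reading.

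A reader might also infer that the pairing is lost, because stage 1 has no subject-level random term although section 10.1 relies on a within-subject correlation. The documents do not support that. The only planned intervals and p-values come from stage 2, which has a subject effect, and no test of the stage 1 group lines is proposed.

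Nor should a reader carry the unchanged-difference argument over to the x-intercept. It holds for slopes in roughly balanced data, not in general for a ratio of two shrunken coefficients.

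**Conclusion.** The concern holds for the slope and, in direction, for the x-intercept. As the protocol is written, the stage 2 intervals are too narrow and the p-values too small. Under the planned model the false-positive rate for slope at nominal 5% runs from 4.7% at reliability 0.99 to 19.4% at 0.64, and the excess is material from about 0.9 downward. These figures assume roughly balanced data, the protocol's means, SDs and correlation, and a range of reliabilities that the documents do not narrow. The upper end must not be read as the plan's actual error rate.

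The consequence specific to this study is the uneven comparison between shrunken slope and x-intercept results and raw TEWL changes. In an exploratory study this should be fixed, but it does not invalidate the design.

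**What to change.** In section 10.3.3 and the matching synopsis text:

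- **Slope.** State that stage 2 uses the unshrunken least-squares slope of each subject-area-day line (five readings), with the Day 0 covariate computed the same way. Keep the planned repeated measures model.
- **SC thickness.** Estimate the x-intercept from the fitted group lines. Obtain the interval for the treated-untreated difference by resampling subjects, keeping both areas of a subject together. Note the small-sample limits of this with about 20 subjects.

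Testing the stage 1 protein-by-treatment term directly is not a substitute. It ignores the pairing and was conservative in the REML check (about 1.8% rejections).

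The cost is somewhat wider intervals and modest programming, with no new data, visits or subjects. One limit remains. If an area-specific difference within a subject persists across days, the planned stage 2 model omits it, and least-squares slopes then rejected in about 7% rather than 5%. That is separate from the shrinkage.

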### **Brief Summary**

It is intended that this study will identify a method capable of measuring improvements in skin barrier function in no more than two weeks. This will be performed by exploring two potential clinical methods to assess barrier repair (1) product use before assessing barrier repair (following tape stripping) "pretreatment" and 2) assessing product use after tape stripping "post-treatment", with observations occurring at various time points). In addition, a statistical method will be explored in the hope that results from it will be more sensitive to changes in barrier function.

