# 8.2 Transepidermal Water Loss (TEWL)

TEWL assessments for barrier function will be performed by a trained technician, using the Tewameter® TM 300 (Courage+Khazaka electronic GmbH) device.

TEWL will be initially measured for each visit, prior to tape stripping (if applicable) for the designated skin site. TEWL will also be performed if tape stripping occurs for the designated skin site / time point after every five tape strips (5, 10, 15 and 20 tape strips) for the pre-treated sites. For the post treatment sites at baseline, TEWL will be repeated post all 20 tape strips.

TEWL is a non-invasive method to measure the integrity of stratum corneum barrier function. Briefly, the measuring principle is based on water vapour gradient determination between two pairs of sensors (temperature and relative humidity) placed at different distances perpendicularly to the skin. The probe will be held in place on the skin for one measurement, for approximately 40 seconds, to ensure that a stable value has been established. The probe should be placed keeping the same orientation of the probe on the subject's skin (relative to horizontal/vertical planes) for all measurements. The first part of the measurement belongs to the equilibration phase. The values of the last 20 seconds are averaged as the actual measurement values. TEWL values will be expressed in gram/square metre/hour (g/m²/hr). An increase in TEWL values shows damage to the skin barrier function.

Subjects will be acclimatised in a relatively stable environment (temperature 21 °C  $\pm$  2 °C, room humidity 50 %  $\pm$  10 %) for a period of at least 30 minutes before each measurement session.

The measurements will be performed on the designated leg skin site for each specific time point. The measurements will be taken in duplicate, on different parts of the test site so the measured parts do not overlap, and then an average reading will be taken for each test site and time point. The same operator should be used throughout the study for any given measurement, in order to reduce the variability. If not possible, then it should be recorded which operator did which measurements

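### Unstripped right-leg TEWL is read at every visit but is not an analysed measure, so the planned analyses do not show whether the stripping-based measures are more sensitive than TEWL alone

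*Protocol*

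**What the plan says.** Section 10.3.3 of the protocol evaluates several parameters "in order to ascertain the most sensitive measure to use in future studies". The Brief Summary in the synopsis adds that "a statistical method will be explored in the hope that results from it will be more sensitive to changes in barrier function", without naming a comparator.

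For the right leg (pre-treatment method), Section 8.2 states that "TEWL will be initially measured for each visit, prior to tape stripping (if applicable) for the designated skin site". Table 1 of the synopsis assigns a new pair of sites, one treated and one untreated, to each of the seven visits. Section 8.3 says that no area is stripped twice. Each subject therefore contributes seven paired readings of intact skin, six of them after baseline.

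The right-leg analyses in 10.3.3 are:
- a 1/TEWL regression on cumulative protein, from which "individual subject estimates of slope and x-intercept will be obtained" and passed to a treatment-by-day model;
- the change in TEWL from before stripping to after 20 strips, in a model of the same kind.

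On the left leg, all post-baseline TEWL is read on the site stripped at Day 0 (Sections 3.2 and 10.3.3). Intact skin is read there at Day 0 only, as a covariate or reference value.

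**The concern.** A study whose product is a choice of measure should include the simplest candidate that it already collects. Pre-strip TEWL on Days 3-14 is neither compared between areas nor summarised. The slope, the x-intercept and the 20-strip rise can be set against each other, but not against a plain reading taken at the same site minutes earlier.

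At stake is the burden of future studies. Twenty strips per site per visit, with protein measured on every disc, are worth carrying forward only if they reveal more than the unstripped reading does. As planned, the results would not speak to that.

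**Working it through.** **1. The plan's own figures.** Section 10.1 gives a slope mean of 3.4 x 10^-5 in magnitude with "standard deviation (SD) approx. 1.4 x 10 -5", and total protein of 3985 µg with SD 1150. It assumes a treated-untreated correlation of 0.5, so the SD of paired differences equals the between-subject SD. A paired t-test with N = 20, two-sided 5%, gives:
- slope: d = 1.1/1.4 = 0.786, power 91.5%; 1.1/3.4 = 32%;
- x-intercept: d = 880/1150 = 0.765, power 90.1%; 880/3985 = 22%.

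Both reproduce the stated 90%. The sample size is sound and the point does not touch it.

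**2. How the measures relate.** The protocol's linear form is 1/TEWL = b(X - p), where b is the slope magnitude (quality), X the x-intercept (thickness) and p the protein removed. For intact skin p = 0, so 1/TEWL = bX. Take b = 3.4 x 10^-5, X = 3985 and, as an assumption, 2000 µg removed by 20 strips:

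| Case | Intact TEWL | 20-strip rise |
|---|---|---|
| Untreated | 7.38 | 7.44 |
| X + 880, slope unchanged | 6.05 (-18%) | 4.22 (-43%) |
| X + 22%, slope reduced in proportion | 7.38 | 5.15 |

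Intact TEWL moves with the product of quality and thickness. It can respond to small gains in both, and it can miss opposing changes. Theory alone does not settle which measure is more sensitive.

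**3. Power on equal terms.** One visit day, N = 20, each measure adjusted for its own Day 0 value (noncentral t, 18 df). N and the area correlation of 0.5 are the protocol's. The following are assumptions:
- slope and thickness are log-normal for the TEWL calculation, and the 0.5 also applies to log TEWL;
- half of the remaining variance persists by area;
- TEWL reading error is 8%;
- slope and x-intercept carry no fitting error, which favours them;
- the slope-thickness correlation r across subjects runs from -0.3 to +0.5.

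Slope and x-intercept: the Day 0 difference correlates 0.5 with the later one, so the SD shrinks by √(1 - 0.5²) = 0.866. For a 15% gain in each:
- slope: d = (0.15 x 3.4/1.4)/0.866 = 0.364/0.866 = 0.421, power 43%;
- x-intercept: d = (0.15 x 3985/1150)/0.866 = 0.520/0.866 = 0.600, power 72%.

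Log pre-strip TEWL: the log variances are ln(1 + (1.4/3.4)²) = 0.1566 and ln(1 + (1150/3985)²) = 0.0800. The paired-difference variance without reading error is v = 0.2366 + 2r(0.396 x 0.283). Reading error adds 2 x 0.08² = 0.0128. The correlation with the Day 0 difference is c = (v/2)/(v + 0.0128), and the adjusted SD is √[(v + 0.0128)(1 - c²)]. The effect is 2 ln 1.15 = 0.2795 when both properties gain 15%, ln 1.32 = 0.278 for quality alone, and ln 1.22 = 0.199 for thickness alone.

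| r | Adjusted SD | Both +15% | Quality +32% | Thickness +22% |
|---|---|---|---|---|
| -0.3 | 0.378 | 88% | 87% | 61% |
| 0 | 0.440 | 77% | 76% | 48% |
| +0.3 | 0.494 | 67% | 66% | 40% |
| +0.5 | 0.527 | 61% | 61% | 36% |
| Best of slope and x-intercept | - | 72% (x-intercept) | 97% (slope) | 96% (x-intercept) |

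The last row uses 0.786/0.866 = 0.907 for slope and 0.765/0.866 = 0.884 for x-intercept in the single-property columns. The 20-strip rise is left out because its power depends on the share of the stratum corneum removed, which the protocol does not give.

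**The case against.** The strongest reply is that the protocol sets out to assess two stripping methods, treated against untreated within each, and nowhere claims superiority over plain TEWL. On that view an unstripped reading is a third method and merely an extra endpoint. The premise is correct: a reader might infer a promised comparison with plain TEWL from the Brief Summary, but the text names no comparator. What remains is that Section 10.3.3 seeks the most sensitive measure, and a measure already in hand is outside the set compared.

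A second reply is that the statistical analysis plan can add the model, since Section 10.3 defers further detail to it. It can. But 10.3.3 fixes each measure, model and covariate, including an alternative covariate analysis for the left leg, so the choice of candidates is made here and is not a detail left open.

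Third, the treatment term of the 1/TEWL model is itself the fitted treated-untreated contrast at p = 0 on each day. That is true, but only slope and x-intercept go on to the treatment-by-day stage.

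Finally, in the scenarios for which the study is powered, the planned measures do better. This stands, and it limits the point to one of completeness.

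**Conclusion.** The gap is real and modest. Intact-skin TEWL is collected in pairs at every right-leg visit and is not an analysed measure, so the planned analyses do not show whether stripping gains sensitivity over it.

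Two stronger readings are not supported. One is that the study cannot answer the question: the readings exist, and only the planned analyses are silent. The other is that plain TEWL would be the better measure. With 15% gains in both properties its power of 61-88% straddles the 72% of x-intercept, and the order turns on a slope-thickness correlation that the protocol does not give. With quality alone up 32%, slope (97%) beats it (61-87%). With thickness alone up 22%, x-intercept (96%) beats it (36-61%). These figures rest on the assumptions listed in the working and illustrate an open empirical question. No stated figure is wrong, no planned estimate is biased, and the sample size is unaffected.

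**What to change.** In Section 10.3.3 and the matching synopsis text, add right-leg pre-strip TEWL on Days 3-14, on the log scale, as a further candidate measure. Use the model already planned for the others: treatment, day and treatment-by-day as fixed effects, subject as random effect, and Day 0 pre-strip TEWL of the same area as covariate. Report its standardised treated-untreated effect by day, with a confidence interval, beside those of slope, x-intercept and the 20-strip rise. Present it as a descriptive benchmark and not as a pass/fail rule, since standardised effects are imprecise at N = 20.

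The cost is one more model and a few lines of text. No subject, visit or reading is added.
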